4.2 Criteria for Removal from Study

Criteria for removal from study:

- i) Incomplete MR images,
- ii) Image artifacts

- iii) Adverse reaction to contrast agent,
- iv) Upon request of Patient for exclusion from study
- v) Suspected patients of bone sarcoma or osteomyelitis with incorrect assignment to a pathology.

Patients removed from the study will be replaced in order to reach a total of 10 subjects for each pathology.

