- (B) If we observe a decline in blood pressure during the contrast media injection, we will discontinue the ferumoxytol injection immediately (in the experience of the PI, a transient hypotension represents a possible AE). In case we observe any signs of a potential anaphylactoid reaction (e.g. significant hypotension > 10% with associated tachycardia or bradycardia) during the contrast media injection, the injection will be discontinued immediately. Patients with mild symptoms such as urticaria, pruritus, rhinorrhea, nausea, diaphoresis and/or coughing will be observed for resolution of symptoms or progression. Patients, who show severe and/or progressive symptoms, such as arrhythmias, severe hypotension, breathing difficulties, dizziness or vomiting will be treated immediately by the M.D. on site and the Pediatric Emergency Care team will be

notified for immediate assistance.

Stopping rules for the study:

- (A) In case of any serious AE, that leads to persistent impairment of a study patient, the study will be terminated.
- (B) Anaphylactoid reactions are a possible, but rare side effect of any contrast agent, reported in 1% of patients receiving Gd-based contrast agents and 1% of patients receiving ferumoxytol. In case we observe an increased incidence of severe anaphylactoid reactions, i.e. more than one patient in our limited study population of 20 patients, the study will be terminated.
- (C) According to our statistician, the study population of n=10 patients with sarcomas and n=10 patients with osteomyelitis is already very limited and considered a pilot population to demonstrate major differences in ferumoxytol enhancement of these two pathologies. In the unlikely event, that contrast enhancement reaches a plateau in both pathologies or no enhancement at all is noted in these pathologies on MR scans, neither on T2-weighted MR scans nor on T1-weighted MR scans, the study will be terminated after evaluation of n=6 patients (MR data from n=6 patients should allow evaluation of significant differences between quantitative pre- and post-contrast signal intensities via a t-test).

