7. ADVERSE EVENTS AND REPORTING PROCEDURES

7.1 Potential Adverse Events

The most common adverse reactions ($\geq 2\%$) following administration of Ferumoxytol are diarrhea, nausea, dizziness, hypotension, constipation and peripheral edema. Ferumoxytol may cause serious hypersensitivity reactions including anaphylaxis and/or anaphylactoid reactions. In clinical studies, serious hypersensitivity reactions were reported in 0.2% of subjects receiving Ferumoxytol. Hypotension may follow Ferumoxytol administration. In clinical studies, hypotension was reported in 1.9 % of subjects.

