9.1.1 Relevant Subset

The outcome will be measured on all subjects included in the study.

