11.2 Primary Analysis

11.2.1 Analysis Population

All MR images of the study population will be included in the analysis. In case of missing data or non-adherence to protocol, the subject will be excluded from analysis.

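### Section 4.2(iii) removes and replaces any patient with an adverse reaction to ferumoxytol, including a mild reactor with a full dose and two evaluable scans

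*Combined protocol and SAP*

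**What the plan says.** Section 4.2 gives five grounds for removal. Items (i) and (ii) cover incomplete images and image artifacts. Item (iii) reads, in full, "Adverse reaction to contrast agent". Items (iv) and (v) cover patient request and wrong assignment to a pathology. The section closes with the replacement rule: "Patients removed from the study will be replaced in order to reach a total of 10 subjects for each pathology".

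Section 6 does grade reactions, under the stopping rules for an individual test. Any fall in blood pressure during the injection stops the injection. So does any sign of a possible anaphylactoid reaction, for example "significant hypotension > 10% with associated tachycardia or bradycardia". Severe or progressive symptoms are treated at once. For the rest: "Patients with mild symptoms such as urticaria, pruritus, rhinorrhea, nausea, diaphoresis and/or coughing will be observed for resolution of symptoms or progression".

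On the analysis set, Section 9.1.1 says "The outcome will be measured on all subjects included in the study". Section 11.2.1 says "All MR images of the study population will be included in the analysis", followed by "In case of missing data or non-adherence to protocol, the subject will be excluded from analysis". Neither mentions patients removed for a reaction.

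**The concern.** Item (iii) stands alone. Loss of usable images is already covered by items (i) and (ii), so (iii) does its own work mainly where the images are usable. Section 6 only observes a patient with, say, mild nausea or urticaria. That patient can receive the full dose, complete both MR examinations and supply every measurement the study needs. Under Section 4.2 as written, the patient is nevertheless removed and replaced.

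The replacement is another patient aged 10-21 given ferumoxytol off-label, an agent for which the protocol quotes a 0.2% rate of serious hypersensitivity. The data obtained in return may already be in hand. The stake is therefore unnecessary exposure, together with some doubt about which 10 patients per group are analyzed.

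**Working it through.** **1. Is there a qualifier anywhere?** Sections 4.2, 6, 7.2, 9.1.1 and 11.2.1 were compared.

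- Section 4.2: item (iii) has no severity, dose or evaluability condition.
- Section 6: mild and severe reactions are distinguished, but to govern the injection and clinical care. It does not say that mild reactors remain in the study.
- Section 7.2: covers treatment of the event and reporting to the IRB only.
- Sections 9.1.1 and 11.2.1: refer to subjects included in the study and to the study population, without saying whether a removed reactor belongs to either.

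No qualifier was found.

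**2. Can the case arise?** Section 4 gives a volume of 8.3-13.3 ml and a maximum rate of 10 ml/min, so the shortest injection takes 8.3/10 = 0.83 to 13.3/10 = 1.33 minutes (the plan says 1-2 minutes). Monitoring runs to 90 minutes. A mild reaction can therefore begin after the full dose is in.

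**3. The plan's own power figure.** Section 11.3.2 states 80% power for a difference of 1.33 SD. With a two-sample t-test, 10 per group, 18 degrees of freedom and an assumed two-sided 5% level, the noncentrality is 1.33 × √(10/2) = 2.97 and the power is 0.803. The figure reproduces. Replacement restores 10 per group, so item (iii) does not change it.

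**4. Extra injections.** Let r be the proportion of injected patients who have a mild reaction but a full dose and evaluable scans. If each is replaced, and replacements react at the same rate, the expected number injected to retain 20 is 20/(1 − r). The chance that at least one of the first 20 is affected is 1 − (1 − r)^20. The documents give no r for this setting, so the values below are illustrations.

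| r | Injected, 20/(1 − r) | Extra | Chance of at least one in 20 |
|---|---|---|---|
| 2% | 20/0.98 = 20.4 | 0.4 | 33% |
| 8% | 20/0.92 = 21.7 | 1.7 | 81% |

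The 2% comes from Section 7.1, which lists the reactions seen in at least 2% of subjects: "following administration of Ferumoxytol are diarrhea, nausea, dizziness, hypotension, constipation and peripheral edema". Nausea is the only one that is also on Section 6's observe-only list. The 8% adds diarrhea, constipation and edema at 2% each, assuming no overlap.

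Neither value is a bound. The 2% is a floor for each reaction, so r could be higher. It could also be much lower:

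- The clinical studies described in Section 5.1 are of anemia treatment in chronic kidney disease, with a therapeutic course given there as 1.02 g. This study expects a single 250-400 mg, which is 250/1020 = 25% to 400/1020 = 39% of that.
- The study calendar evaluates adverse events only at the two MRI visits.

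**5. Would a blood pressure fall above 10% alone be a safe removal trigger?** The case report form has a pre-injection reading and five readings from 0 to 60 minutes. Assume, from outside the documents, a systolic mean of 110-120 mmHg, independent reading-to-reading SD of 4-8 mmHg and no drug effect. By simulation, 5% to 42% of patients would show at least one reading more than 10% below the first. In 20 patients that is 1.0 to 8.4. With only two post-injection readings, as the Section 4 text describes, the range is 2% to 25%, or 0.5 to 5.0 of 20. At most of these values, such a trigger would replace more evaluable patients than the 0.4 to 1.7 at issue.

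**The case against.** The strongest reply is that Section 4.2 is a short list meant to be read with Section 6. An investigator who has only observed a mild reaction could reasonably keep a patient with complete scans. The affected group is also narrow. Section 6 stops the injection for any blood pressure decline or possible anaphylactoid sign, and removing a patient with a partial dose is defensible. So is removing a severe or hemodynamic reactor, because Section 2.4 uses the first examination to assess perfusion, blood volume and permeability. Section 6 adds that colleagues saw no blood pressure fall or severe nausea in children with brain tumors, although that does not address mild reactions.

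Much of this stands, and it keeps the point small. It does not supply the missing condition, since Section 6 governs care during the test and Section 4.2 governs who remains in the study.

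A reader might go further and infer that Section 4.2 contradicts Sections 9.1.1 and 11.2.1. The documents do not support that. A removed patient can naturally be read as outside both the included subjects and the study population, so this is an ambiguity only. A reader might also infer that removed reactors drop out of the stopping rules. Section 6 counts severe reactions in a population of 20 and does not say how replaced patients are counted, but nothing says they are ignored.

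**Conclusion.** The point holds as a minor one. As written, Section 4.2(iii) replaces a mild reactor whose dose was complete and whose scans are evaluable, and nothing else in the protocol limits it. This is a stated rule with a slightly worse result than a narrower one would give.

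The cost is about 0.4 extra injections at an illustrative 2% rate. That figure rests on an assumed rate, on every affected patient being removed, and on replacements reacting at the same rate. A loss of power should not be inferred. Nor do the documents establish that the removed patient's images are discarded: replacement to reach 10 suggests it, but the text does not say so.

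**What to change.** Reword 4.2(iii) along these lines: *Adverse reaction that led to incomplete injection or incomplete MR, or a severe reaction (treatment required, or a blood pressure fall above 10% accompanied by tachycardia or bradycardia, as in Section 6) before or during post-contrast imaging.*

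Do not use a blood pressure fall above 10% alone. Section 6 uses that threshold in two ways: as a dose-reduction trigger when it occurs unexpectedly in more than one patient, and, paired with a heart-rate change, as an example of a possible anaphylactoid sign. Neither makes a lone fall a reason to remove one patient.

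Patients with a mild reaction, a full dose and evaluable images stay among the 10 per group and are flagged. Add a sentence that everyone given any ferumoxytol counts in the Section 6 stopping rules and the safety report, and one in 11.2.1 saying whether images of removed patients are analyzed.

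The cost is one reworded criterion and two sentences. No new fields are needed, because the case report form already records whether the injection was complete, the actual volume, vital signs to 90 minutes, and the time and description of any reaction. The downside is that a few analyzed patients will have had a mild reaction, which the flag makes visible.

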4.3 Alternatives

The current alternative diagnostic methods are: biopsy, which is invasive, painful, and frequently inadequate; MRI, with significant overlap/difficulty in distinguishing between the two entities without an iron nanoparticle contrast; PET/CT/X-ray, which are even more difficult to distinguish and include exposure to ionizing radiation. The current standard of imaging is an MRI, which is included in our study; the addition of an iron nanoparticle contrast agent is expected to make this a much more efficacious diagnostic tool.

The conduct of our research should actually improve the speed with which the participants receive the most appropriate therapy, as we expect to be able to distinguish much more quickly between the differentials for the symptoms the patient's experience.

5. INVESTIGATIONAL AGENT/DEVICE/PROCEDURE INFORMATION

5.1 Investigational Agent/Device/Procedure

Study Agent:

Ferumoxytol (Feraheme™) represents a novel USPIO compound that has been recently FDA-approved for intravenous treatment of iron deficiencies in patients with renal failure (6). Ferumoxytol nanoparticles have a mean hydrodynamic diameter of 30 nm and are composed of an iron oxide core and a hydrophilic synthetic coating (6). Ferumoxytol exerts strong signal effects on MR images, as quantified by a high r_1 relaxivity of 38 $\text{L mmol}^{-1} \text{ s}^{-1}$ and a high r_2 relaxivity of 83 $\text{L mmol}^{-1} \text{ s}^{-1}$ at 20 mHz (9). Ferumoxytol has been applied as a contrast agent for MR imaging of arthritis in an animal model (9) and imaging of glioblastomas in patients (10). To the best of our knowledge, ferumoxytol has not been investigated for MR imaging of bone sarcomas or osteomyelitis. In MR imaging Ferumoxytol shortens the relaxation times for nearby hydrogen atoms. This effect can be imaged with appropriate MR pulse sequences.

Indication and Usage: Ferumoxytol is used as an iron replacement product indicated for the treatment of iron deficiency anemia in adult patients with chronic kidney disease.

We propose an off label application of Feraheme as a MRI contrast agent.

Mechanism of Action: Ferumoxytol consists of a superparamagnetic iron oxide that is coated with a carbohydrate shell, which helps to isolate the bioactive iron from plasma components until the iron-carbohydrate complex enters the reticuloendothelial system macrophages of the liver, spleen and bone marrow. The iron is released from the iron-carbohydrate complex within vesicles in the macrophages. Iron then either enters the intracellular storage iron pool (e.g., ferritin) or is transferred to plasma transferrin for transport to erythroid precursor cells for incorporation into hemoglobin. In MR imaging Ferumoxytol shortens the relaxation times for nearby hydrogen atoms. This effect can be imaged with appropriate MR pulse sequences.

Animal Studies: Animal studies demonstrate that the plasma half-life of Ferumoxytol increased with increasing dose. The highest tissue concentration of ferumoxytol was found in the liver, spleen and central lymphnode pool. Studies with radio-labeled drug product demonstrated that the renal elimination of iron in ferumoxytol was insignificant, while the carbohydrate coating was significantly excreted in urine and feces. Repeat dose toxicity studies of ferumoxytol in rats (cumulative exposure approximately 12 times the anticipated exposure of a human therapeutic course of 1.02 g of ferumoxytol on mg/m^2 basis) and dogs (cumulative exposure approximately 40 times the anticipated exposure of a human therapeutic course of 1.02 g of ferumoxytol on mg/m^2 basis) demonstrated dose dependent decreases in body weight gain and food consumption, and increases in pigmentation intensity. No systemic toxicity or immunotoxicity was observed at relevant clinical doses.

Clinical Studies: The safety and efficacy of Ferumoxytol for the episodic treatment of iron deficiency anemia in patients with CKD were assessed in three randomized, open-label, controlled clinical trials.

Ferumoxytol is not currently approved for diagnostic imaging applications. It is being evaluated as an agent for vascular enhanced MRI (VE-MRI). In August 2008 the FDA granted Fast track designation to ferumoxytol for its development as a diagnostic agent for VE-MRI to improve assessment of peripheral arterial disease in patients with known or suspected chronic renal disease (CKD). The fast track process is designed to facilitate the development and expedite the FDA's review of products. AMAG-sponsored Phase I/IIa studies have been completed and results published (36, 37, 38, and 39). Doses of 0.4-2 mg/kg in normal volunteers demonstrated arterial and venous vessels in several body regions (36). VE-MRI effectively identified aortic root incompetence in 6 subjects (37). In another reported study, 11 subjects with a variety of vascular disease who were scheduled for clinically indicated angiography, doses 1 to 4 mg/kg (38). In this study ferumoxytol imaging was done using a variety of pulse sequences. The study confirmed the ability to perform imaging of different arterial segments. An additional publication showed promise in the evaluation of deep venous thrombosis (39). Several additional studies on vascular imaging of the cerebral and pelvic arterial circulations have been conducted under physician-sponsored investigational new drug applications. In a study of patients with central

nervous system disease, Ferumoxytol in doses of 1 to 4 mg/kg was compared with non-contrast time-of-flight MRI, Gadolinium-enhanced MRI and VE-MRI (40). Ferumoxytol, with its persistence in vasculature due to its low vascular permeability and long intravascular half-life, provided better estimates of cerebral perfusion than gadolinium, and differences in biomarker properties were considered to be clinically advantageous in evaluating 12 patients with malignant brain tumors (40).

Clinical Pharmacokinetics: Ferumoxytol exhibits dose-dependent, capacity-limited elimination from plasma with a half life of approximately 15 hours in humans.

Major route of elimination: Ferumoxytol is slowly cleared from blood by tissue macrophages (liver, spleen, lymph node and active bone marrow) over 2-3 months. The macrophages release the iron to body iron stores where it can be incorporated into hemoglobin.

Drug Interactions: Ferumoxytol may reduce the absorption of concomitantly administered oral iron preparations.

Adverse Reactions: The most common adverse reactions ($\geq 2\%$) following administration of Ferumoxytol are diarrhea, nausea, dizziness, hypotension, constipation and peripheral edema. Ferumoxytol may cause serious hypersensitivity reactions including anaphylaxis and/or anaphylactoid reactions. In clinical studies, serious hypersensitivity reactions were reported in 0.2% of subjects receiving Ferumoxytol. Hypotension may follow Ferumoxytol administration. In clinical studies, hypotension was reported in 1.9 % of subjects.

Dose: Single intravenous injection of Ferumoxytol during the first MRI scan, at a dose of 5 mg Fe/kg.

The delivered iron dose via a typical ferumoxytol administration is in the order of 150-500 mg iron oxides (note that these are coated iron particles, not free iron), which is equivalent to or lower than the iron dose administered with one blood sample.

Study Device:

MR Scanner, 1.5T and 3 T, GE healthcare. MRI with and without contrast is a non-significant risk exam, as defined by the FDA and IRB guidelines.

5.2 Availability

The study drug will be purchased from AMAG, Manufacturer

5.3 Agent Ordering

The agent will be ordered by research administrator [name].

5.4 Agent Accountability

The investigational drug will be kept secure and locked with [name].

6. DOSE MODIFICATIONS

Dose modification scheme:

- (A) Serious anaphylactoid reactions are not dose dependent. Thus, in case we should observe an increased incidence of severe anaphylactoid reactions, i.e. more than one patient in our limited study population of 20 patients, or if any of our patients encounters a permanent impairment due to the ferumoxytol administration, the study will be terminated.
- (B) In case we should observe an unexpected decrease in blood pressure of more than 10% in more than one patient via blood pressure measurements or in case we observe severe nausea in more than one patient, we will successively decrease the administered dose by 1 mg/kg until event-free tolerance is achieved. Of note, our colleagues from Oregon Health & Science University (see below) reported no such side effects of ferumoxytol in their population of children with brain tumors.
- (C) Precontrast MR scans will serve as an internal standard. We will measure the signal intensity of sarcomas and osteomyelitis and divide this signal by the signal of normal muscle to normalize for potential MR spectrometer variations over time. We expect at least 20% tumor/muscle enhancement on post-contrast T2-weighted MR scans compared to precontrast scans. If this enhancement will not be achieved, but ferumoxytol is well tolerated, we will increase the administered dose to 6 mg Fe/kg with a maximum total amount of 510 mg Fe (FDA-approved dose for single injection).
- (D) In the unlikely event, that the T1- and T2-enhancement of both pathologies exceeds 500%, we have reached a plateau of contrast agent accumulation for both pathologies rather than depicting an expected relative limited accumulation of ferumoxytol in sarcomas compared to osteomyelitis. Based on our experience with pre-clinical and clinical iron oxide applications, we expect that maximal difference between sarcomas and osteomyelitis occur with the highest dose. This is the reason why we limit our study population to this dose for this initial pilot study. In the unlikely event that contrast agent accumulation reaches a plateau in both of these pathologies or no enhancement is noted on MR scans, we will terminate the study after evaluation of n=6 patients (MR data from n=6 patients should allow evaluation of significant differences between quantitative pre- and post-contrast signal intensities via a t-test). We have submitted an R21 NIH grant proposal which would allow more extensive evaluation of patient subgroups (n=5), examined with decreasing ferumoxytol doses.

Stopping rules for an individual test:

- (A) To avoid paravasal injections, the peripheral venous access will be checked with a saline flush prior to contrast media injection. In case of any swelling or discoloration at the ferumoxytol injection site (in the extremely rare event of a paravasal injection despite prior uncomplicated saline injection), the ferumoxytol injection will be stopped immediately, a new peripheral venous access will be placed at the contralateral extremity and the remaining ferumoxytol will be slowly administered. In case a local reaction is observed again, the ferumoxytol injection will be discontinued completely.
- (B) If we observe a decline in blood pressure during the contrast media injection, we will discontinue the ferumoxytol injection immediately (in the experience of the PI, a transient hypotension represents a possible AE). In case we observe any signs of a potential anaphylactoid reaction (e.g. significant hypotension > 10% with associated tachycardia or bradycardia) during the contrast media injection, the injection will be discontinued immediately. Patients with mild symptoms such as urticaria, pruritus, rhinorrhea, nausea, diaphoresis and/or coughing will be observed for resolution of symptoms or progression. Patients, who show severe and/or progressive symptoms, such as arrhythmias, severe hypotension, breathing difficulties, dizziness or vomiting will be treated immediately by the M.D. on site and the Pediatric Emergency Care team will be

notified for immediate assistance.

Stopping rules for the study:

- (A) In case of any serious AE, that leads to persistent impairment of a study patient, the study will be terminated.
- (B) Anaphylactoid reactions are a possible, but rare side effect of any contrast agent, reported in 1% of patients receiving Gd-based contrast agents and 1% of patients receiving ferumoxytol. In case we observe an increased incidence of severe anaphylactoid reactions, i.e. more than one patient in our limited study population of 20 patients, the study will be terminated.
- (C) According to our statistician, the study population of n=10 patients with sarcomas and n=10 patients with osteomyelitis is already very limited and considered a pilot population to demonstrate major differences in ferumoxytol enhancement of these two pathologies. In the unlikely event, that contrast enhancement reaches a plateau in both pathologies or no enhancement at all is noted in these pathologies on MR scans, neither on T2-weighted MR scans nor on T1-weighted MR scans, the study will be terminated after evaluation of n=6 patients (MR data from n=6 patients should allow evaluation of significant differences between quantitative pre- and post-contrast signal intensities via a t-test).

